### 7.2 Demographic and other baseline characteristics

7.2.1.	Subject	background
--------	---------	------------

Target	FAS		
population:			
Items:	Age (at time of consent acqu	isition), height,	weight, clinical classification, diagnosis,
	HPV genotype, HPV 16 E7 n	nolecule protein	expression level (absolute quantification
	value) before start of admini	stration, and H	PV E7-specific immune response before
	start of administration (total =	eight items).	
Categories	Clinical classification: inpatie Diagnosis: HSIL/CIN2, HSIL HPV genotype: positive for H	nt, outpatient //CIN3 IPV16 only, HP	V16+other types
	HPV16 E7 molecule protein	expression lev	el (absolute quantification value) before
	start of administration		
	HPV E7-specific immune re	sponse before s	start of administration, 16 and 24 weeks
	after the first dose		
Analysis	Tabulation is conducted for ea	ach group accor	ding to the data type of each item, and the
content:	uniformity of the distribution is confirmed. The significance level of the test was not		
	specified, and only the p-valu	e of the test is s	hown.
	Item	Data type	Analysis content
	A an haight weight	Continuous	Cummony statistics Knusles W-11!-

Item			Data type	Analysis co	ontent	
Age,	height,	weight,	Continuous	Summary	statistics,	Kruskal–Wallis
HPV16	E7	molecule		test		

protein expression level (absolute quantification value) before start of		
administration		
Clinical classification,	Binary	Number of cases, percentage,
diagnosis, HPV genotype,		chi-squared test
HPV16 E7 molecule		
protein expression level		
(absolute quantification		
value, two categories)		
before start of		
administration		
HPV16 E7 molecule	Three	Number of cases, percentage,
protein expression level	categories	Kruskal–Wallis test
(absolute quantification		
value, three categories)		
before start of		
administration		

#### Definition:

"Unknown" and "missing"

When there are either "unknown" or "missing" variables in the target variables, they are not distinguished and both handled as "unknown." The "unknown" classification is displayed only when there are applicable subjects. It should be included in the denominator of the percentage calculation and excluded from the test.

7.2.2. Concomitant drugs and therapies

FAS Target

population:

Calculate the number of cases and percentages for each concomitant drug and Analysis concomitant therapy used from the first dose of the trial drug to the end of the trial for content: each group.

Definition: • Exclude from the tabulated subjects those whose start day is after Day 112 (16 weeks after the first dose) or whose end day is before Day 1.

> • In tabulations of concomitant drugs and concomitant therapies (both generic names), cases where multiple drugs / therapies that correspond to the same generic name are used will be tabulated as a single drug / therapy.

7.2.3 Therapy compliance status

FAS Analysis

target:	
Analysis	Calculate the number of cases and percentages of the following items for each group.
content:	• Completed number of courses: four courses, three courses, two courses, one course,
	zero courses.
	• Drug compliance rate: "less than 80%;" "80% or more." Separately calculate
	summary statistics for each group as continuous values.
	• Presence or absence of discontinuation of trial drug use.
Definition:	Drug compliance rate (%)=100×[total number of sticks taken/(20*3)]
7.2.4 Trial di	rug exposure status
Analysis	Safety analysis set
target:	
Analysis	Conduct the same analysis as in Section 7.2.5.
content	

#### 7.3 Efficacy analysis

7.3.1.	Analysis of primary endpoint		
The prim	ary efficacy endpoint is the regression rate at 16 weeks after the first dose.		
7.3.1.1.	Primary analysis		
Target	FAS		
populatio	on:		
Analysis	1) Estimation of the regression rate for each group		
content:	Calculate the regression rate and its 95% confidence interval (Clopper-Pearson		
	method) for each group. Conduct the same analysis by stratification by the		
	following five factors:		
	Diagnosis: "HSIL/CIN2;" "HSIL/CIN3"		
	• HPV genotype: "HPV16 only" "HPV16+other types"		
	Facilities: four facilities		

- HPV16 E7 molecule protein expression level before start of administration.
- HPV E7-specific immune response (spot-forming cell: SFC/10^6 cells)

2) Pairwise comparison between each dose group and placebo group

Pairwise comparisons of low-dose group vs. placebo group, intermediate-dose group vs. placebo group, and high-dose group vs. placebo group are conducted by Fisher's exact test.

3) Evaluation of the dose-response relationship by the maximum contrast method. The following six contrasts are set for the dose-response relationships of the placebo group, low-dose group, intermediate-dose group, and high-dose group: (1) [-1.5, -0.5, 0.5, 1.5], (2) [-3, 1, 1, 1], (3) [-2, 0, 1, 1], (4) [-1, 3, -1, -1], (5) [-1, -1, 3, -1], and (6) [-1, -1, -1, 3]. The p-value for each contrast is calculated, and the dose-response relationship with the lowest p-value is identified. Specifically, the contrasting components of (1)-(6) are investigated using a logistic model in which the presence or absence of a response is set as the response variable and the dose group is the explanatory variable.

Definition: • The judgment categories for the histopathological regression indicators of cervical intraepithelial neoplasia, which is the basis of response judgment, are set as "CR," "PR," "SD," "PD," and "No judgment." Here, "No judgment" includes the following: "not judgeable" for reasons such as the histological test specimen being too small or diagnosis being difficult because of specimen preparation; missing judgment result because a test was not conducted.
• Regression rate (%)=100×(number of response cases / number of FAS cases).
• Multiplicity adjustments are not conducted for 2) and 3).

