### 6. Statistical analysis policy

### 6.1 Significance level and confidence level

Unless otherwise specified, tests are two-sided tests with a significance level of 0.05, and the confidence interval is a two-sided confidence interval with a confidence coefficient of 95%.

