### 6.2 Multiplicity adjustment

Given that this trial is a phase I/II trial, multiplicity was not considered in either pairwise comparisons or dose-response evaluations using the maximum contrast method of the response rate, which is the primary efficacy endpoint, between each dose group and the placebo group. Additionally, multiplicity of tests will not be considered when tests are repeated for secondary endpoints.

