#### 4) Effect of HSIL/CIN 2-3 lesions on cytology

For FAS and PPS, for subjects diagnosed with HSIL at registration, the percentages of "PR," "SD," "PD," and "No judgment" are calculated for each group at weeks 16 and 24. The denominator of the percentage (%) of each judgment is the number of cases in the analysis set. Furthermore, for the FAS, the same tabulation is conducted by stratification using stratification factors.

5) Percentages of "CR," "PR," "SD," and "PD" in the histopathological evaluation indicators of cervical intraepithelial neoplasia

For FAS and PPS, the percentages of "CR," "PR," "SD," and "PD," and "No judgment" are calculated for each group at weeks 16 and 24. The denominator of the percentage (%) of each judgment is the number of cases in the analysis set. Furthermore, for the CR rate, Fisher's exact test is used for pairwise comparisons between each dose group and the placebo group. Additionally, the dose-response relationship is investigated with the same contrasts as in Section 7.3.1.1). For FAS, the same tabulation is conducted by stratification using the stratification factors.

6) Evaluation of changes in the HPV genotype

For FAS and PPS, the percentages of the number of cases for judgment categories ("negative," "positive, but not including type 16," "HPV16 only," "HPV16+other types," and "no judgment") are calculated for each group at weeks 16 and 24, with the number of cases for each judgment of "HPV16 only" and "HPV16+other types" before trial drug administration. Separately, the number and percentage of cases is calculated for the category of "clearance of HPV16" by merging "negative" and "positive, but not including HPV16." Furthermore, for FAS, the same tabulation is conducted by stratification using the stratification factors.

7) Disease control rate

For FAS and PPS, the percentage of subjects with histology of CIN3 at

registration improving to CIN2 or lower at weeks 16 and 24 is calculated for each group, and their 95% confidence intervals (Clopper–Pearson method) are calculated. Additionally, Fisher's exact test is used for pairwise comparisons between each dose group and the placebo group. Furthermore, for FAS, the same tabulation is conducted by stratification using the stratification factors.

Definition:

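### The dose-response step picks the lowest of six raw two-sided p-values without regard to sign, so it can name a shape the data contradict, and the selected p-value is not a calibrated 5% test

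*SAP*

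**What the plan says.** SAP Section 7.3.1.1 item 3), part of the primary analysis in the FAS, names the maximum contrast method. It lists contrasts over placebo, low, intermediate and high dose: "1) [-1.5, -0.5, 0.5, 1.5], (2) [-3, 1, 1, 1], (3) [-2, 0, 1, 1], (4) [-1, 3, -1, -1], (5) [-1, -1, 3, -1],"; the sixth is [-1, -1, -1, 3]. They are evaluated "using a logistic model in which the presence or absence of a response is set as the response variable", with dose group as the explanatory variable. The selection rule is "The p-value for each contrast is calculated, and the dose-response relationship with the lowest p-value is identified".

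Section 6.1 sets the default: "tests are two-sided tests with a significance level of 0.05". Item 3) gives no other level, no direction and no reference distribution for the maximum.

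Adjustment is waived twice. Section 6.2, citing the phase I/II status, says "multiplicity was not considered in either pairwise comparisons or dose-response evaluations using the maximum contrast method of the response rate". The definitions in 7.3.1.1 repeat it: "Multiplicity adjustments are not conducted for 2) and 3".

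The same contrasts are reused for the CR rate in Section 7.3.2 item 5), where "the dose-response relationship is investigated with the same contrasts as in Section 7.3.1.1". The primary endpoint text in Section 4.1 makes dose-response and the choice of a recommended dose the primary objective.

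**The concern.** There are two separate weaknesses.

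**Direction.** A two-sided p-value is small whether the contrast estimate is large and positive or large and negative. Ranking six shapes on two-sided p-values can therefore select a shape because the data run opposite to it. The output would then name a pattern such as all doses better than placebo when every dose did worse. This is a fault of the selection rule whatever one thinks about multiplicity.

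**Calibration.** The smallest of six correlated p-values is smaller than a single p-value would be by chance. A maximum contrast test normally deals with this by comparing the largest statistic with its own null distribution. The SAP keeps the name of the method but leaves out that step, so the p-value attached to the selected shape does not carry the 5% meaning of Section 6.1.

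At stake is how the dose-response result is read in a trial whose primary objective is dose-response.

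**Working it through.** **Inputs from the SAP.** Four groups of 41, 164 in total (Section 3.3), allocated 1:1:1:1 (Section 3.2); the six contrasts and the lowest-p rule (7.3.1.1); two-sided 0.05 (6.1). The SAP states no overall error rate for this step, so there is no figure of its own to reproduce.

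**Assumptions.** The SAP gives no response rate, so a common rate of 10% to 50% is assumed. It does not name the test statistic, so Wald contrasts from the logistic model with dose group as a factor are used. All 41 per group are analysed.

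**Step 1: can a shape be selected against its own direction?** Take 15, 6, 8, 7 responders of 41 (36.6%, 14.6%, 19.5%, 17.1%).

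- Log odds, ln[x/(41-x)]: -0.550, -1.764, -1.417, -1.580.
- Variances, 1/x + 1/(41-x): 0.1051, 0.1952, 0.1553, 0.1723.
- Contrast (2): estimate = -3(-0.550) - 1.764 - 1.417 - 1.580 = -3.111.
- Standard error = sqrt(9 x 0.1051 + 0.1952 + 0.1553 + 0.1723) = 1.212.
- z = -3.111/1.212 = -2.57, two-sided p = 0.010.

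| Contrast | z | p |
|---|---|---|
| (1) | -1.63 | 0.104 |
| (2) | -2.57 | 0.010 |
| (3) | -2.19 | 0.028 |
| (4) | -1.18 | 0.239 |
| (5) | -0.26 | 0.794 |
| (6) | -0.71 | 0.476 |

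All six estimates are negative, and contrast (2) is identified. A second case: 12, 3, 10, 11 of 41 gives contrast (4), the low-dose peak, the lowest p (z = -2.42, p = 0.015), because the low dose was worst.

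**Step 2: how often is the lowest p below 0.05 with an inert drug?** In large samples the six z-values are jointly normal, with the correlations implied by the coefficients. From 4,000,000 draws, P(max |z| > 1.96) = 18.2%. Six independent tests would give 1 - 0.95^6 = 26.5%, which is only an upper reference. With 41 per group (at least 400,000 simulated trials per rate; trials with an empty cell counted as non-significant):

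| Assumed common rate | P(lowest p < 0.05) | Share of these with negative sign |
|---|---|---|
| 10% | 12.7% | 28% |
| 15% | 16.0% | 34% |
| 20% | 17.1% | 39% |
| 30% | 17.7% | 44% |
| 40% | 17.9% | 47% |
| 50% | 18.6% | 50% |

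At 20%, wrong-sign selections with p < 0.05 occur in about 0.171 x 0.39 = 6.7% of null trials. Each contrast taken alone is close to nominal (4.5-5.2% at rates of 20-50%), so the excess comes from selection.

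**Step 3: what would calibrate it?** The joint null distribution puts the two-sided 5% cut at |z| of about 2.51 (raw p about 0.012). If only positive contrasts may be selected, the one-sided 0.025 cut is z of about 2.53. With 41 per group that cut gives 2.2-2.6% at rates of 15-50%. A sign condition alone is not enough: one-sided 0.025 without adjustment still gives 10-11% with 41 per group.

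**Step 4: CR rate only.** Every contrast has a non-zero placebo coefficient. If Wald tests were used and placebo had no CR, all six would be uninformative: with 0, 8, 10, 12 CRs of 41, Fisher's test of high dose against placebo gives p = 0.0002, while all six Wald p-values exceed 0.99. The chance of no CR on placebo is 0.95^41 = 12.2% at an assumed CR rate of 5%, and 0.92^41 = 3.3% at 8%.

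**The case against.** The strongest reply is that the lack of adjustment is disclosed, reasoned and consistent. Section 6.2 gives the phase I/II setting as its reason, 7.3.1.1 agrees, and no controlled overall error rate is claimed. That stands: a reader might infer an overlooked multiplicity error, and the text does not support this.

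Nor does item 3) say that a dose-response is shown when the lowest p-value is below 0.05. It only identifies a shape; the threshold comes from the default in Section 6.1. So the 16-19% is the error from reading the selected p-value at that default, not an error rate the plan declares. If the p-values only rank shapes, the calibration point weakens. The direction point does not, because the ranking itself can name the wrong shape.

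It is also fair that items 1) and 2) report each group's rate with its confidence interval and three Fisher tests, so a placebo-best result would be visible. That limits the harm but leaves the dose-response output contradicting the tables beside it. A reader might further infer that the selected contrast alone fixes the recommended dose. The SAP does not say so; Section 2 pairs dose determination with safety.

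On empty cells, the SAP does not specify Wald tests, and likelihood-ratio contrasts do not fail in the example above. For the primary endpoint at rates of 15% or more, an empty placebo arm has a chance of at most 0.85^41, about 0.13%. A general failure of the primary analysis is therefore not supported.

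**Conclusion.** The point holds in two parts. First, the selection rule ignores direction, so as written it can identify a shape the data contradict; the phase I/II waiver concerns multiplicity and does not cover this. Second, the p-value of the identified contrast is not a calibrated 5% test. Read at 0.05, it gives a false dose-response in about 16-19% of trials of an inert drug for response rates of 15-50% and about 13% at 10%. Roughly a third to a half of the false signals at 15-50% have a negative sign.

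These figures rest on assumed response rates, Wald contrasts and 41 analysed per group; the large-sample value of 18.2% needs no assumed rate. It would be too strong to say that the plan commits itself to a 17% error rate, or that most null trials flagged point to harm. The empty-cell issue is minor, conditional on Wald tests, and confined to the CR rate. The change is advisable, but the point does not invalidate the rest of the primary analysis.

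**What to change.** In Section 7.3.1.1 item 3):

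- Keep the six contrasts and report all raw p-values with the sign of each estimate.
- Allow only a contrast with a positive estimate to be identified.
- Beside the raw p-value, report the maximum-contrast p-value from the joint distribution (multivariate normal or permutation) of the positive maximum. Name the level: one-sided 0.025, z of about 2.53, matches two-sided 0.05 testing.
- If that level is not met, state that no dose-response was shown.
- Name the test statistic. For the CR rate in 7.3.2 item 5), use likelihood-ratio, Firth-penalised or permutation contrasts so that an arm without events can be handled.

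Amend the waiver in both places, Section 6.2 and the closing definition in 7.3.1.1, so that they agree: the three pairwise Fisher tests can stay unadjusted, and the dose-response evaluation is taken out. Changing only one would create a contradiction.

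The cost is SAP wording and a short program, with no new data. The drawback is that the p-value reported for the identified contrast becomes less favourable.

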### 3.2 Randomization

Registered subjects will be randomized in a 1:1:1:1 ratio for each of the four dose groups. The following three factors are used as allocation adjustment factors.

- 1. Diagnosis (HSIL/CIN2, HSIL/CIN3)
- 2. HPV genotype (HPV16 only, HPV16+other types)
- 3. Facilities (four facilities)

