### 3.3 Target sample size

The sample includes 164 cases, with 41 cases each for the placebo group, low-dose group (0.5 g/administration/day), intermediate-dose group (1.0 g/administration/day), and high-dose group (1.5 g/administration/dose). Each group will have 10 cases with HSIL/CIN2 at the time of registration. See Section 5.2 of the trial protocol for the setting basis.

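### The primary between-group tests use none of the factors on which allocation is balanced, which leaves each pairwise comparison conservative and costs some power

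*SAP*

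**What the plan says.** - **Allocation (SAP 3.2).** The four groups are allocated equally, and the balancing is stated as follows: "The following three factors are used as allocation adjustment factors". These are diagnosis, HPV genotype (HPV16 alone or with other types) and facility (four).
- **Size and mix (SAP 3.3).** "The sample includes 164 cases, with 41 cases each for the placebo group" and for each of the other groups. On diagnosis, the section adds: "Each group will have 10 cases with HSIL/CIN2 at the time of registration".
- **Level (SAP 6.1).** Unless otherwise specified, "tests are two-sided tests with a significance level of 0.05".
- **Pairwise tests (SAP 7.3.1.1, item 2).** The three dose-versus-placebo comparisons "are conducted by Fisher's exact test", with no stratification.
- **Dose-response (SAP 7.3.1.1, item 3).** The six contrasts are examined by logistic regression, where response status "is set as the response variable and the dose group is the explanatory variable". No other covariate is named.
- **Where the factors do appear (SAP 7.3.1.1, item 1).** Regression rates with Clopper-Pearson intervals are given per group within strata. This is estimation only, and 7.3.1.2 drops it for the per-protocol set.
- **Reuse (SAP 7.3.2, items 1 and 5).** The 24-week regression rate takes over the primary analysis. The CR rate takes over Fisher's test and the same contrasts.

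**The concern.** Balancing on a prognostic factor makes the groups more alike than simple randomization would. A test that ignores the factor still counts the variation between its strata as noise, so it rejects too rarely under the null and loses power under the alternative. Fisher's exact test on 41 against 41 is already conservative because its p-values are discrete, and the two effects add.

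The SAP gives some reason to think diagnosis matters. It is the first allocation factor and its count per group is fixed. Under the primary endpoint definition in section 4.1, a CIN3 lesion that falls to CIN2 is still stable disease, so a CIN3 case must fall further than a CIN2 case to count as a response. The trial has to judge three doses against placebo with 41 subjects each, and power given up in the test brings nothing in return.

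**Working it through.** **The plan's own figures.** 4 × 41 = 164, as stated. CIN2 share: 10/41 = 24%, leaving 31 CIN3 per group. The SAP states no power, response rate or effect size and refers the basis to protocol section 5.2, so no planned power can be reproduced.

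**Inputs from the SAP.** 41 per group, 10 CIN2 and 31 CIN3, two-sided 0.05.

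**Assumed inputs (not in the SAP).** Four pairs of placebo regression rates, a common treatment odds ratio of 3.67 within diagnosis, exact 10/31 balance, and all 41 per group in the full analysis set.

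**Rates implied.** Active odds = 3.67 × placebo odds. For placebo 40% (CIN2) and 10% (CIN3):
- Active CIN2: 3.67 × 0.667 = 2.447, i.e. 71.0%. Active CIN3: 3.67 × 0.111 = 0.408, i.e. 29.0%.
- Overall placebo: (10 × 0.40 + 31 × 0.10)/41 = 17.3%. Overall active: (10 × 0.710 + 31 × 0.290)/41 = 39.2%.
- Diagnosis odds ratio: (0.40/0.60)/(0.10/0.90) = 6.0. For the other pairs it is 9.0 (50/10), 3.9 (30/10) and 3.8 (40/15).

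**Tests compared.** With a and b responders in the two groups and m = a + b:
- Fisher's exact test on the pooled 2×2 table.
- Unstratified Pearson: X² = 82(a − b)² / [m(82 − m)].
- CMH by diagnosis, no continuity correction: X² = [Σ(a_k − m_k/2)]² / Σ[m_k(N_k − m_k) / (4(N_k − 1))], with N_k = 20 for CIN2 and 62 for CIN3.

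Pearson sits in the middle on purpose. The step from Fisher to Pearson uses no covariate. The step from Pearson to CMH is the adjustment.

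**Power, % (200,000 replicates per scenario; an exact enumeration of the tables agrees to a fraction of a point).**

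| Placebo CIN2/CIN3 | Fisher | Pearson | CMH | Fisher to Pearson | Pearson to CMH | Total |
|---|---|---|---|---|---|---|
| 40/10 | 51.6 | 61.1 | 66.4 | 9.5 | 5.3 | 14.8 |
| 50/10 | 46.6 | 56.4 | 65.5 | 9.8 | 9.1 | 18.9 |
| 30/10 | 54.9 | 64.1 | 66.4 | 9.2 | 2.3 | 11.5 |
| 40/15 | 63.2 | 71.7 | 73.9 | 8.5 | 2.2 | 10.7 |

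**Size under the null, same scenarios.** Fisher about 1.5 to 2.3%, Pearson 3.1 to 4.7%, CMH 4.8 to 4.9%. The CMH gain is therefore not bought with excess type I error. Pearson's 3.1% (at 50/10) shows the effect of omitting diagnosis without Fisher's discreteness.

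**Two controls.**
- No prognostic effect (placebo 20% in both diagnoses): a gap of 7.5 points between Fisher and CMH remains, although there is nothing to adjust for.
- CMH with continuity correction: 55.9, 54.3, 55.9 and 65.1% in the order of the table, only 4.3, 7.7, 1.0 and 1.9 points above Fisher.

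**Wider range.** A second simulation used placebo rates of 10 to 30%, active rates of 30 to 60% and diagnosis odds ratios of 1 to 10. Its CMH test was stratified by diagnosis and genotype together, with an assumed genotype mix and genotype odds ratios of 1 to 4. The total gain was 4 to 20 points. Adjustment contributed −1 to +9: at most 2.5 with a diagnosis odds ratio of 3 or less, and above 5 only with one near 10.

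**The case against.** **Is the choice defensible?** Fisher's test is valid at any sample size, and the SAP contradicts nothing by using it. This is a phase I/II trial that deliberately leaves multiplicity unadjusted (SAP 6.2). With 10 CIN2 cases per group, crossing diagnosis with genotype leaves small cells. All of this stands. It makes the point an improvement in efficiency, not the correction of an error.

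**Readings that go too far.**
- *Ignoring the factors costs the whole 11 to 19 points.* A reader might infer this from the Fisher-to-CMH gap. The Pearson column rules it out: in three of the four scenarios Fisher's discreteness accounts for well over half, and in the fourth for about half.
- *All the primary tests run at about 2%.* That size belongs to a single Fisher comparison. The logistic contrasts do not share Fisher's discreteness. In a null simulation with 17 to 30% response, the linear contrast alone rejected at 4.2 to 4.9%, and at least one of the six unadjusted contrasts at about 17%. At least one of the three Fisher tests rejected at about 7%.
- *Genotype and facility carry a known loss.* They are omitted too, but no separate gain was computed for either, and none for the logistic contrasts.
- *The factors never enter any test in the plan.* SAP 7.3.2, item 3 repeats Wilcoxon comparisons within strata for E7 expression. The statement holds for the tests of regression and CR rates.
- *The SAP shows diagnosis to be strongly prognostic.* It gives no response rate by diagnosis. The strength is an assumption, and the adjustment gain depends on it.

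**Conclusion.** The point holds as an inexpensive gain in efficiency. It is certain from the SAP that allocation uses three factors and that the primary tests of the regression rate use none. The size is conditional. Under the assumed rates (placebo 30 to 50% in CIN2 and 10 to 15% in CIN3, odds ratio 3.67, full 10/31 balance), changing the pairwise test to an uncorrected CMH test stratified by diagnosis gains about 11 to 19 points of power. Roughly 8 to 10 of these come from leaving an exact discrete test. Roughly 2 to 9 come from using diagnosis, near 9 only if the diagnosis odds ratio is about 9. If diagnosis is weakly prognostic, the adjustment itself adds little. If the continuity-corrected form is used, the whole gain falls to about 1 to 8 points. The plan's tests remain valid, with no inflation of a single comparison's error rate.

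**What to change.** - **SAP 7.3.1.1, item 2.** Make each dose-versus-placebo test a CMH test stratified by diagnosis, stated to be without continuity correction. Report the stratified risk difference with its 95% confidence interval. Keep Fisher's exact test as a sensitivity analysis.
- **SAP 7.3.1.1, item 3.** Add diagnosis as a covariate to the logistic model that carries the six contrasts, and HPV genotype if its cells are not sparse.
- **SAP 7.3.2, items 1 and 5.** Apply the same to the 24-week regression rate and the CR rate.
- **Facility.** Say in one sentence why it is left out of the tests if it stays out.

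The cost is SAP wording and a few lines of code, with no new data. The downside is reliance on a large-sample test and possibly sparse strata. Stratifying on diagnosis alone and keeping the Fisher analysis deal with both. The change should be fixed before unblinding.
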